8.1.5 Complication

A complication is defined as an SADE that requires an invasive intervention or leads to death.

8.1.6 MRI scan related complication

A complication is deemed to be MRI related if it is caused by or related to the interaction between the RV high voltage lead, Ellipse VR ICD and the MRI system that occurs during the MRI scan and includes the time the subject is within the 5 Gauss line of the MRI system, or up through the subject's 1 month post MRI scan follow up visit. The MRI scan related complications will be based on the CEC adjudication data.

8.2 Procedure for assessing, recording and reporting adverse device effects, serious adverse device effects and UADEs (for US sites) and USADEs (for OUS sites):

Safety surveillance within this study and the safety reporting, both performed by the investigator, starts as soon as the subject is enrolled in the study. Enrollment occurs after the subject signs the main study consent, meets all of the inclusion and none of the exclusion criteria verified during the pre-MRI testing, and the MRI Settings have been programmed. . The safety surveillance and the safety reporting will continue until the last investigational visit has been performed, the subject is deceased, the subject/investigator concludes his participation into the study or the subject/investigator withdraws the subject from the study, except as otherwise specified in the CIP.

Once the patient completes the pre-MRI visit testing and the MRI Settings have been programmed according to the protocol, all adverse device effects (whether serious or not-serious) UADEs and USADEs will be collected and reported to the Sponsor on an Adverse Event case report form through the EDC system.

8.2.1 Criteria and guidelines for non-reportable events

Except as otherwise noted in the CIP, the following events are not reportable to the sponsor:

Clinical Investigational Plan

- Events not related to the procedure to remove, replace or reposition the study lead or ICD.
- Unavoidable events, as listed in Table 3: Unavoidable events related to the MRI Scan that resolve within the timeframes specified

8.2.2 Criteria and guidelines for reportable events

Records relating to the subject's subsequent medical course must be maintained and submitted (as applicable) to the Sponsor until the event has subsided or, in case of permanent impairment, until the event stabilizes and the overall clinical outcome has been ascertained. Adverse events will be monitored until they are adequately resolved. The status of the subject's condition should be documented at each visit.

The investigator will report the event to the IRB/EC per their reporting requirements.

Reportable events to sponsor are considered:

- ADEs, SADEs, and UADEs (for US sites) and USADEs (for OUS sites) caused by or associated with the study MRI scan (except unavoidable events related to the MRI scan)
- Unavoidable ADEs whose conditions worsen or continue beyond the time frame listed in the Unavoidable events tables.
- All ADEs, SADEs and UADEs(for US sites)/USADEs (for OUS sites) that are not associated with the MRI scan

All above events will be reported to the Sponsor, as soon as possible, but no later than 72 hours of first learning of the event. A list of foreseeable adverse events and anticipated adverse device effects include, but are not limited to, those listed in Table 2: Anticipated Events and Anticipated Adverse Device Effects. Refer to section 3.3 for full details.

The Sponsor will ensure that all adverse events are reported to the relevant authorities as per regulations. The description of the adverse event, date of the adverse event, treatment and resolution of the reportable adverse events will be reported, as applicable, to the relevant authorities per regulations. Additional information may be requested, when required, by the Sponsor in order to support the reporting of AE CRFs to regulatory authorities.

The investigator must notify the IRB, if appropriate, in accordance with national and local laws and regulations, of the AE CRFs reported to the Sponsor.

Clinical Investigational Plan

8.2.3 Preliminary Safety Report

A preliminary report of all adverse event data will be sent to FDA by the Sponsor after the first 20 subjects complete their one month post MRI scan visit. In addition, the Sponsor will also report to the FDA if five or more subjects experience a worsening of pacing capture threshold, as defined by the primary endpoint.

8.3 Subject Death

8.3.1 Procedure for recording and reporting subject death

All subject deaths are to be documented and reported to the sponsor within 72 hours after becoming aware of the event.

The Clinical Events Committee (CEC) (see section 14.1) reviewing adverse device effects noted in sections 8.1.2-8.1.6 for the study will also review and classify all potential subject deaths. All subject deaths that occur during this investigation must be reported to St. Jude Medical as soon as possible. Notification of death should include a detailed statement of the pertinent events and be signed by the investigator in addition to the appropriate case report forms (Death CRF, Withdrawal CRF, and Product Out of Service CRF). It is the investigator's responsibility to notify the IRB per the IRB policy. Details of death and the following information, if available, should be provided in a letter to St. Jude Medical by the investigator summarizing the subject's course since enrollment in the study:

- Date and time of death
- Place death occurred (e.g. hospital, nursing home, subject's home)
- If death was witnessed
- Identification of the rhythm at the time of death, if known (include any available documentation)
- Cause of death
- Any other circumstances surrounding the death
- Approximate time interval to death from the initiating event.
- Autopsy report (if performed)
- Whether it was device and/or procedure related
- Whether it was related to the study
- Device configuration at the time of death

If any of the above information is not available, provide an explanation in the death narrative of what attempts (and how many) were made to obtain the information, and the outcome of those attempts. At a minimum, two (2) phone calls should be placed, followed by a certified letter, to the subject's next of kin. Provide clinical notes and

Clinical Investigational Plan

witness statements. If possible, interrogate the ICD. Retrieve and print all episode diagnostics, IEGMs, and programmed parameters.

Every attempt should be made to explant the ICD and/or leads intact. Any explanted devices or leads should be returned to St. Jude Medical for analysis promptly. In the event that the device is not explanted, the above procedure must be followed to retrieve the data. The reason the ICD and/or lead(s) are not being returned to St. Jude Medical must be stated clearly on the case report form.

8.4 Complaint

A complaint is defined as an inadequacy of a medical device with respect to its identity, quality, durability, reliability, safety or performance. Complaints may be submitted from the time of consent through the end of the study.

If a complaint involves an adverse device effect category or death as described in the protocol (section 8.1-8.3), then the investigator shall notify the Sponsor by completing the adverse event or death case report form as applicable and must provide the Sponsor with all necessary documentation needed.

If the complaint does not involve a reportable adverse event per protocol the investigator should notify the SJM Product Surveillance Department through one of the methods listed below as soon as possible after becoming aware of a complaint.

Email address: [contact]

Toll Free: [contact]

Direct US: [contact]

Complaints will be collected and reported by St. Jude Medical according to our product reporting process.

9.0 Data Management

Overall, the Sponsor will be responsible for the data handling. The sponsor and/or its affiliates will be responsible for compiling and submitting all required reports to governmental agencies.

Data will be analyzed by the Sponsor and may be transferred to the Sponsor's locations outside of the US and/or any other worldwide regulatory authority in support of a market-approval application.

Clinical Investigational Plan

St. Jude Medical respects and protects personally identifiable information that we collect or maintain. As part of our commitment, St. Jude Medical is certified in the U.S. - European Union Framework and U.S. – Swiss Safe Harbor Framework Agreements regarding human resources and subject clinical trial personal information. The privacy of each subject and confidentiality of his/her information will be preserved in reports and when publishing any data. Confidentiality of data will be observed by all parties involved at all times throughout the clinical study. All data will be secured against unauthorized access.

An electronic data capture (EDC) system will be used to collect data and store data specified in the CIP. This data collection includes all data points found on the electronic case report forms (eCRFs) for the study. The EDC system may also be used to upload source documents related, but not limited to AE CRFs and deaths.

The Principal Investigator or institution will provide direct access to source data during and after the clinical study for monitoring, audits, IRB/EC review and regulatory authority inspections. As required, the Principal Investigator or institution will obtain permission for direct access to source documents from the subject, hospital administration and national regulatory authorities before starting the clinical study.

9.1 Data Management Plan

A detailed Data Management Plan (DMP) will be established to ensure consistency of data collection. This document will include procedures used for data review, database cleaning, and issuing and resolving data queries. If appropriate, the DMP may be updated throughout the study duration. All revisions will be tracked and document controlled.

CRF data will be captured in a validated electronic database management Oracle Clinical system hosted by St. Jude Medical. Only authorized site personnel will be permitted to enter the data through the electronic data capture (EDC) system deployed by St. Jude Medical. An electronic audit trail will be used to track any subsequent changes of the entered data.

9.2 Document and Data Control

9.2.1 Traceability of documents and data

The investigator will ensure accuracy, completeness, legibility and timeliness of the data reported to the sponsor on the CRFs and in all required reports.

9.2.2 Recording Data

Source documents will be created and maintained by the investigational site team throughout the clinical study.

Clinical Investigational Plan

The data reported on the CRFs will be derived from, and be consistent with, these source documents, and any discrepancies will be explained in writing.

All data reported for the study must be substantiated with source documentation in the subject's medical records, clinic records or other forms of documentation provided by or approved by Sponsor.

The CRFs will be validated (eCRF) by the authorized site personnel. .

10.0 Monitoring

It is the responsibility of St. Jude Medical as the sponsor of the study to ensure the study is conducted, recorded, and reported according to the approved protocol, subsequent amendment(s), applicable regulations, and guidance documents. Monitoring will be conducted according to the St. Jude Medical Clinical Monitoring standard operating procedure.

Prior to beginning the study, St. Jude Medical will contact the investigator or designee to discuss the study and data requirements. A St. Jude Medical monitor will periodically review the subject records and associated source documents.

The investigator shall make subject and study records available to the clinical monitor for monitoring.

11.0 Regulatory Inspections

The investigator and/or delegate should contact St. Jude Medical immediately upon notification of a governmental agency inspection at the site. A clinical monitor or designee will assist the investigator and/or delegate in preparing for the audit.

An investigator who has authority to grant access will permit authorized governmental agency employees, at reasonable times and in reasonable manner, to enter and inspect any establishment where devices are held (including any establishment where devices are used or where records or results are kept).

An investigator, or any person acting on behalf of such a person with respect to the study, will permit authorized governmental agency employees, at reasonable times and in reasonable manner, to inspect and copy all records relating to the study.

An investigator will permit authorized governmental agency employees to inspect and copy records that identify subjects, upon notice that governmental agency has reason to suspect that adequate informed consent was not obtained, or that reports required to be submitted by

Clinical Investigational Plan

the investigator, to the Sponsor or IRB/EC have not been submitted or are incomplete, inaccurate, false or misleading.

12.0 Statistical considerations

The following section presents statistical considerations for the study. Additional details on statistical analyses are maintained in a separate Statistical Analysis Plan (SAP).

12.1 Statistical design, hypotheses, method and analytical procedures

Note: In the statistical section below, all references to MRI are referring to the study MRI scan.

12.1.1 Primary Safety endpoint

The primary safety endpoint #1 is: Freedom from MRI scan-related complications related to the Ellipse VR ICD involving Durata or Optisure (RV) lead from MRI scan to 1 month post MRI scan testing.

Hypothesis

The hypothesis is formally expressed as:

$$H_0: p_S \leq 90\%$$

$$H_a: p_S > 90\%$$

where p_S is the freedom from MRI scan-related complications(s) for the Durata or Optisure RV lead from MRI scan to 1 month after the MRI scan.

Analysis

The primary analysis will be conducted on subjects who meet all of the following criteria:

- Implanted with St. Jude Medical Durata or Optisure (RV) Lead
- Sign informed consent
- Meet the MRI Conditions of Use
- Undergo a Study MRI scan
- Have 1 month post-MRI scan visit or have MRI-scan related complication(s) for the Ellipse VR ICD involving Durata or Optisure RV lead before the 1 month post MRI visit

Clinical Investigational Plan

The hypothesis will be tested at the 2.5% significance level. The null hypothesis will be rejected if the 97.5% lower confidence bound for p_S is greater than 90%. The 97.5% lower confidence bound will be calculated by the exact (Clopper-Pearson) method for binomial probabilities.

12.1.2 Primary Efficacy Endpoint #1 (Change in Capture Threshold for Durata and Optisure (RV) Leads)

The primary efficacy endpoint #1 is the proportion of Durata or Optisure (RV) leads implanted with the Ellipse VR ICD with capture threshold increase of $\leq 0.5V$ at 0.5ms from pre-MRI scan to 1 month post-MRI scan testing.

Hypothesis

Success is defined as ventricular capture threshold increase of $\leq 0.5V$ at 0.5ms for the Durata or Optisure (RV) lead from pre-MRI scan testing to 1 month post-MRI scan.

The hypothesis is formally expressed as:

$$H_0: p_{E1} \leq 90\%$$

$$H_a: p_{E1} > 90\%$$

where p_{E1} is the probability of success.

Analysis

The primary analysis will be conducted on subjects who meet all of the following criteria:

- Implanted with the Durata or Optisure RV lead and Ellipse VR ICD
- Sign Informed consent
- Meet the MRI Conditions of Use
- Undergo a Study MRI scan
- Have MRI visit data for right ventricular capture threshold
- Have 1 month post-MRI scan visit data for RV capture threshold
- Have not undergone any VR ICD lead repositioning or replacement since the MRI scan up to 1 month post-MRI scan

The hypothesis will be tested at the 2.5% significance level. The null hypothesis will be rejected if the 97.5% lower confidence bound for p_{E1} is greater than 90%. The 97.5% lower confidence bound will be calculated by the exact (Clopper-Pearson) method for binomial probabilities

Clinical Investigational Plan

12.1.3 Primary Efficacy Endpoint #2 (Change in Sensing Threshold for Durata and Optisure (RV) leads)

The primary efficacy endpoint #2 is the proportion of Durata or Optisure (RV) leads implanted with the Ellipse VR ICD with sensing amplitude decrease of $\leq 50\%$ from pre-MRI scan testing to 1 month post-MRI scan.

Hypothesis

Success is defined as ventricular sensing amplitude decrease of $\leq 50\%$ from pre-MRI scan testing to 1 month post-MRI scan. The hypothesis is formally expressed as:

$$H_0: p_{E2} \leq 87\%$$

$$H_a: p_{E2} > 87\%$$

where p_{E2} is the probability of success.

Analysis

The primary analysis will be conducted on subjects who meet all of the following criteria:

- Implanted with the Durata or Optisure RV lead and Ellipse VR ICD
- Sign informed consent
- Meet the MRI Conditions of Use
- Undergo a Study MRI scan
- Have MRI visit data for RV sensing threshold
- Have 1 month post-MRI scan visit data for RV sensing threshold
- Have not undergone any VR ICD lead repositioning or replacement since the MRI scan up to 1 month post-MRI scan
- Have an intrinsic heart rate ≥ 30 beats per minute at the time of ventricular capture threshold measurements

The null hypothesis will be tested at the 2.5% significance level. The null hypothesis will be rejected if the 97.5% lower confidence bound for p_{E2} is greater than 87%. The 97.5% lower confidence bound will be calculated by the exact (Clopper-Pearson) method for binomial probabilities.

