
 • Lead electrode heating and tissue damage resulting in loss of sensing or capture or both • Lead heating resulting in thrombus formation or embolism • Device heating resulting in tissue damage in the implant pocket or subject discomfort or both • Induced currents on leads resulting in continuous capture, VT/VF, hemodynamic collapse, or all three • Damage to the device or leads causing: 
 a. the system to fail to detect or treat irregular heartbeats b. the system to treat the subject’s condition incorrectly • Damage to the functionality or mechanical integrity of the device resulting in the inability of the device to communicate with the programmer • Movement or vibration of the device or leads • Lead dislodgment • Competitive pacing and potential for VT/VF induction due to ambulatory asynchronous pacing in MRI mode • Pulmonary Embolism 	
These risks are mitigated through the selection of investigators who are qualified by training and/or experience to evaluate and treat subjects implanted with an ICD system.
 
In addition, study investigators will be trained on the study protocol to ensure the proper procedures are followed to assure subject safety during the study MRI scan. This includes continuous monitoring of the subject using pulse oximetry, ECG and verbal communication during the scan.
 
Advanced Cardiac Life Support (ACLS) procedures will be in place to address situations where a life threatening arrhythmia and/or hemodynamic collapse occurs. The programmer will be used outside the American College of Radiology (ACR) defined Zone 4 magnet room. If the subject’s hemodynamic function is compromised during the MRI scan, the MRI scan will be stopped, and proper measures will be taken to restore the subject’s hemodynamic function.

Potential ICD Related Events	

 • Refer to the Ellipse user’s manual for a full list of potential adverse events 	
The Ellipse VR ICD is a market-released ICD. The adverse events associated with this ICD are the same as those associated with other market-released ICDs.
 
These risks are mitigated through the

Clinical Investigational Plan

Event	Mitigation
	selection of investigators who are qualified by training and/or experience to evaluate and treat subjects implanted with an ICD.
Potential Lead Related Events	

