12.2 Sample size

12.2.1 Sample size for primary safety endpoint

In the St. Jude Medical Accent MRI pacemaker IDE study, the results of which were submitted in PMA 60067410/A, and another manufacturer's study involving an MRI conditional pacemaker, the complication-free rate was observed to be 100%.^{16,14}

Therefore, the sample size is calculated under the conservative assumption of

Clinical Investigational Plan

complication-free rate of 97%. Under this assumption, a sample size of 141 subjects will provide 90% power to reject the null hypothesis at a 2.5% significance level. The sample size was calculated using the exact binomial method in SAS® v9.4.

12.2.2 Sample size for primary efficacy endpoint #1 (Change in capture threshold for Durata or Optisure (RV) lead)

In the St. Jude Medical Accent MRI pacemaker IDE study, the results of which were submitted in PMA 60067410/A, the proportion of leads with an increase in threshold ≤ 0.5 volts from pre-MRI scan testing to 1-Month after the MRI scan was 100%.^{1,2}. Therefore, the sample size is calculated under the conservative assumption of 98% for the endpoint. Under this assumption, a sample size of 85 subjects will provide 80% power to reject the null hypothesis at a 2.5% significance level. The sample size was calculated using the exact binomial method in SAS® v9.4.

12.2.3 Sample size for primary efficacy endpoint #2 (Change in sensing threshold in Durata or Optisure (RV) lead)

In the St. Jude Medical Accent MRI pacemaker IDE study, the results of which were submitted in PMA 60067410/A, the proportion of leads with ‘ventricular sensing amplitude decrease of $\leq 50\%$ from pre-MRI scan testing to 1-Month after the MRI scan,’ was approximately 97%. Therefore, the sample size is calculated under the conservative assumption of 95% success rate for the ventricular sensing threshold endpoint. Under this assumption, a sample size of 118 subjects will provide 80% power to reject the null hypothesis at a 2.5% significance level. The sample size was calculated using the exact binomial method in SAS® v9.4.

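### Both primary efficacy sets drop any lead revised between scan and 1 month whatever the cause, so a lead revised because the MRI dislodged it or its capture or sensing deteriorated is removed, not counted as a failure

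*Combined protocol and SAP*

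**What the plan says.** Each efficacy analysis set (12.1.2 for capture, 12.1.3 for sensing) lists among its entry conditions that subjects "Have not undergone any VR ICD lead repositioning or replacement since the MRI scan up to 1 month post-MRI scan". The condition applies after exposure and does not mention cause. Each set also needs a 1-month value; for capture the condition is "Have 1 month post-MRI scan visit data for RV capture threshold". An explanted lead has no such value, so it drops out as well.

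The safety set in 12.1.1 is built differently. A subject enters with a 1-month visit "or have MRI-scan related complication(s) for the Ellipse VR ICD involving Durata or Optisure RV lead before the 1 month post MRI visit". A qualifying event before 1 month therefore stays in and counts against the endpoint.

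Table 2 in 3.3 lists the potential MRI-related events. They include "Lead electrode heating and tissue damage resulting in loss of sensing or capture or both" and "Lead dislodgment".

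Sections 12.8 to 12.10 (use of all data, missing data and withdrawals, exclusions for hypothesis testing) refer to a separate SAP, which is not part of the supplied text.

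**The concern.** Capture and sensing are what the two efficacy endpoints measure, and Table 2 names their loss as a possible effect of the scan. A lead with a moderate deterioration stays in and is scored as a failure. A lead bad enough to be repositioned or replaced within the month leaves the analysis. The exclusion can therefore be a consequence of the outcome, and it removes the worst results first.

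The bias has a condition. It arises only if revised leads would have failed the 0.5 V or 50% criterion more often than the others. That is to be expected when the reason is dislodgment or loss of capture or sensing. It is not expected when the reason has nothing to do with lead performance.

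At stake is whether each efficacy proportion describes all scanned leads or only those that did not need revision, and whether the 2.5% error rate holds for each endpoint.

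**Working it through.** **Inputs from the protocol.** Performance goals p0 are 90% (capture) and 87% (sensing). The test is an exact Clopper-Pearson 97.5% lower bound (12.1.2, 12.1.3). Planned success rates are 98% and 95%, and 12.2.1 assumes a "complication-free rate of 97%. Under this assumption, a sample size of 141 subjects will provide 90% power" for safety. The dataset is frozen at 141 subjects with a 1-month visit (12.2.5).

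**The plan's own figures.** The exact binomial method reproduces the stated sample sizes of 85, 118 and 141. Attained power is 90.9%, 86.3% and 93.7%, at or above the stated 80%, 80% and 90%. The sample sizes are not in error.

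**Pass limits.** The most failures that still pass are:
- capture: 7 at n = 141, and 6 at n = 130 to 140;
- sensing: 10 at n = 138 to 141, and 9 at n = 130 to 137;
- safety: 7 at n = 141.

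**Cases where the exclusion reverses the result** (141 scanned leads):

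| Endpoint | Failures | All counted | Excluded | After exclusion |
|---|---|---|---|---|
| Capture | 8 | 133/141, bound 89.13%, fails | 1 | 133/140, 89.97%, fails |
| Capture | 8 | 133/141, bound 89.13%, fails | 2 | 133/139, 90.84%, passes |
| Sensing | 11 | 130/141, bound 86.47%, fails | 1 | 130/140, 87.26%, passes |

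**How likely such counts are at the planned rates.** P(8 or more of 141 at 2%) = 0.8% for capture. P(11 or more of 141 at 5%) = 9.7% for sensing. At the 97% sensing success observed in the prior study cited in 12.2.3, the latter is 0.4%.

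**False-pass probability at the goal.** Let r be the share of scanned leads that fail and are revised and excluded. The protocol gives no value, so r is an assumption. Let F ~ Bin(141, 1 − p0) be the true failures and d ~ Bin(F, r/(1 − p0)) those excluded. The endpoint passes if F − d is within the limit at n = 141 − d. Summing over F and d:

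| r | Mean leads excluded (141 × r) | Capture | Sensing |
|---|---|---|---|
| 0 | 0 | 2.4% | 1.9% |
| 0.5% | 0.7 | 2.6% | 2.8% |
| 1% | 1.4 | 3.2% | 4.0% |
| 2% | 2.8 | 6.3% | 7.0% |
| 3% | 4.2 | 13.1% | 11.5% |

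The 3% row uses the plan's whole safety allowance (100% − 97%), so it is the upper end.

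**With the safety endpoint also required to pass.** Suppose every excluded lead is also a safety failure and there are no others, so that d ≤ 7 is needed as well. At r = 1%, 2% and 3% the joint figures are 3.2%, 6.2% and 12.1% (capture) and 4.0%, 7.0% and 10.8% (sensing). They hardly change because safety still passes with probability P(Bin(141, 0.03) ≤ 7) = 93.7% at a 3% complication rate.

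**The case against.** **Safety already counts the worst cases.** Under 8.1.5, "A complication is defined as an SADE that requires an invasive intervention or leads to death", and an MRI-related lead revision meeting that definition is a failure in a co-primary endpoint that must pass (12.3). This stands in part. Safety tolerates 7 of 141, and under 8.1.6 "The MRI scan related complications will be based on the CEC adjudication data". A revision for a raised threshold that is not adjudicated MRI-related counts against neither safety nor efficacy. Passing safety also leaves the reported efficacy proportions uncorrected.

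**A moved lead's 1-month value no longer describes the scanned position.** Correct, and that measurement should not be used. This does not justify dropping the lead when the scan, or loss of the measured function, prompted the revision.

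**The SAP may deal with it.** Sections 12.8 to 12.10 defer these topics, so nobody can say from the supplied text that a sensitivity analysis is missing. The primary sets, however, are defined in the protocol. A SAP that scored these leads as failures in the primary analysis would contradict it.

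**Other safeguards exist.** Significant threshold rises are reported as adverse device effects (6.5.2.2, 6.5.3.1), leads are measured directly after the scan, FDA is told if five or more subjects worsen in capture (8.2.3), and a DSMB reviews the data (14.2). These make deterioration visible but do not alter the primary proportions.

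**The event may be rare or absent.** The prior pacemaker studies cited in 12.2.1 were 100% complication-free. The 3% scenario turns every allowed complication into a lead revision that also fails the endpoint, and it exceeds the 2% total capture failure rate that the plan expects. This stands and limits the severity.

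**Conclusion.** The point holds in conditional form. As written, the efficacy sets can remove leads because they failed, and the protocol avoids this for safety but not for efficacy. At an assumed 0.5% to 1% of leads failing and being revised, the inflation is small. It becomes material only at 2% to 3%, which are upper scenarios. All these figures assume 141 leads in each set before exclusion, true success exactly at the goal, and every excluded lead a failure on the endpoint in question.

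A reader might infer that any lead revision biases efficacy upward, or that the 13.1% and 11.5% figures are the expected error rates. The documents support neither. Revisions unrelated to lead performance add little or no bias, no revision rate is given, and it may be zero. Nor do the documents show that the study could succeed while ignoring MRI damage altogether, since adjudicated MRI-related complications still count in safety. Severity is minor to should-fix.

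**What to change.** Change the analysis-set wording in 12.1.2 and 12.1.3, and the SAP to match:

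- Do not use the post-revision measurement.
- Keep the lead and score it as a failure for both endpoints when the CEC adjudicates the repositioning, replacement or explant as MRI-related.
- Otherwise, keep it and score it as a failure for the endpoint concerned when the documented reason is loss or deterioration of that measure: capture in 12.1.2, sensing in 12.1.3. A lead revised only for sensing loss should not become a capture failure, or the reverse.
- Exclude only other revisions.
- If the SAP does not already contain one, add a sensitivity analysis that counts all excluded revised leads as failures.

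No extra subjects or visits are needed. Section 6.8 already asks for a System Revision CRF when a lead is replaced or repositioned, and 6.8.2 generally keeps revised subjects to the 1-month visit. The reason for revision must be recorded; the CRFs are held separately, so whether that is a new item is unknown. CEC work grows only if revisions outside its present remit are sent to it. The downside is that observed success may be slightly lower. The rule should be fixed before outcome data are seen, since choosing it later would be post hoc.
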